No	-
Yes	-
Lacune on imaging	
Not visible	-
Visible	-
WMH or hypoattenuation	
Not visible	-
Visible	-

SVD score	
0	-
1	-
>1	-

† Minimisation variable

Figure 2b. Forest plot for cilostazol versus none of composite outcome (stroke, TIA, MI, cognitive impairment, dependency or death) by clinical and adjudicated imaging subgroups. Adjusted

	Interaction p
Age †	
<60	-
60-69	-
≥70	-
Sex †	
Female	-
Male	-
Highest education †	
A-level (equivalent) or higher	-
O-level/GCSE (equivalent)	-
Primary or secondary primary school	-
Pre-morbid mRS †	
0	-
1	-
>1	-
Time stroke-baseline †	
<180 days	
180-364 days	
≥365 days	
Smoking	
Never	-
Past	-
Present	-
Hypertension	
No	-
Yes	-
Diabetes mellitus	
No	-
Yes	-
History of stroke or TIA	
No	-
Yes	-
Systolic BP †	
<130	-
130-159	-
≥160	-
NIHSS †	
0/1	-
>1	-
Relevant acute infarct on imaging	
No	-
Yes	-
Lacune on imaging	
Not visible	-
Visible	-
WMH or hypoattenuation	
Not visible	-
Visible	-
SVD score	

0	-
1	-
>1	-

† Minimisation variable

Figure 2c. Forest plot for combined isosorbide mononitrate and cilostazol versus neither of composite outcome (stroke, TIA, MI, cognitive impairment, dependency or death) by clinical and adjudicated imaging subgroups. Adjusted

	Interaction p
Age †	
<60	-
60-69	-
≥70	-
Sex †	
Female	-
Male	-
Highest education †	
A-level (equivalent) or higher	-
O-level/GCSE (equivalent)	-
Primary or secondary primary school	-
Pre-morbid mRS †	
0	-
1	-
>1	-
Time stroke-baseline †	
<180 days	
180-364 days	
≥365 days	
Smoking	
Never	
Past	
Present	
Hypertension	
No	-
Yes	-
Diabetes mellitus	
No	-
Yes	-
History of stroke or TIA	
No	-
Yes	-
Systolic BP †	
<130	-
130-159	-
≥160	-
NIHSS †	
0/1	-
>1	-
Relevant acute infarct on imaging	
No	-
Yes	-
Lacune on imaging	
Not visible	-
Visible	-
WMH or hypoattenuation	
Not visible	-
Visible	-
SVD score	

0	-
1	-
>1	-

† Minimisation variable

Figure 3a. Forest plot of 7 level cognition scale for isosorbide mononitrate versus none at 12 months by clinical and adjudicated imaging subgroups. Adjusted

	Interaction p
Age †	
<60	-
60-69	-
≥70	-
Sex †	
Female	-
Male	-
Highest education †	
A-level (equivalent) or higher	-
O-level/GCSE (equivalent)	-
Primary or secondary primary school	-
Pre-morbid mRS †	
0	-
1	-
>1	-
Time stroke-baseline †	
<180 days	
180-364 days	
≥365 days	
Smoking	
Never	
Past	
Present	
Hypertension	
No	-
Yes	-
Diabetes mellitus	
No	-
Yes	-
History of stroke or TIA	
No	-
Yes	-
Systolic BP †	
<130	-
130-159	-
≥160	-
NIHSS †	
0/1	-
>1	-
Relevant acute infarct on imaging	
No	-
Yes	-
Lacune on imaging	
Not visible	-
Visible	-
WMH or hypoattenuation	
Not visible	-
Visible	-
SVD score	

0	-
1	-
>1	-

† Adjustment variable

Figure 3b. Forest plot of 7 level cognition scale for cilostazol versus none at 12 months by clinical and adjudicated imaging subgroups. Adjusted

	Interaction p
Age †	
<60	-
60-69	-
≥70	-
Sex †	
Female	-
Male	-
Highest education †	
A-level (equivalent) or higher	-
O-level/GCSE (equivalent)	-
Primary or secondary primary school	-
Pre-morbid mRS †	
0	-
1	-
>1	-
Time stroke-baseline †	
<180 days	
180-364 days	
≥365 days	
Smoking	
Never	
Past	
Present	
Hypertension	
No	-
Yes	-
Diabetes mellitus	
No	-
Yes	-
History of stroke or TIA	
No	-
Yes	-
Systolic BP †	
<130	-
130-159	-
≥160	-
NIHSS †	
0/1	-
>1	-
Relevant acute infarct on imaging	
No	-
Yes	-
Lacune on imaging	
Not visible	-
Visible	-
WMH or hypoattenuation	
Not visible	-
Visible	-
SVD score	

0	-
1	-
>1	-

† Adjustment variable

Figure 3c. Forest plot of 7 level cognition scale for combined isosorbide mononitrate and cilostazol versus neither at 12 months by baseline subgroups. Adjusted

	Interaction p
Age †	
<60	-
60-69	-
≥70	-
Sex †	
Female	-
Male	-
Highest education †	
A-level (equivalent) or higher	-
O-level/GCSE (equivalent)	-
Primary or secondary primary school	-
Pre-morbid mRS †	
0	-
1	-
>1	-
Time stroke-baseline †	
<180 days	
180-364 days	
≥365 days	
Smoking	
Never	
Past	
Present	
Hypertension	
No	-
Yes	-
Diabetes mellitus	
No	-
Yes	-
History of stroke or TIA	
No	-
Yes	-
Systolic BP †	
<130	-
130-159	-
≥160	-
NIHSS †	
0/1	-
>1	-
Relevant acute infarct on imaging	
No	-
Yes	-
Lacune on imaging	
Not visible	-
Visible	-
WMH or hypoattenuation	
Not visible	-
Visible	-
SVD score	

0	-
1	-
>1	-

† Adjustment variable

Figure 4a. Forest plot of Wei-Lachin global outcome for isosorbide mononitrate versus none by subgroups. Adjusted

	Interaction p
Age †	
<60	-
60-69	-
≥70	-
Sex †	
Female	-
Male	-
Highest education †	
A-level (equivalent) or higher	-
O-level/GCSE (equivalent)	-
Primary or secondary primary school	-
Pre-morbid mRS †	
0	-
1	-
>1	-
Time stroke-baseline †	
<180 days	
180-364 days	
≥365 days	
Smoking	
Never	
Past	
Present	
Hypertension	
No	-
Yes	-
Diabetes mellitus	
No	-
Yes	-
History of stroke or TIA	
No	-
Yes	-
Systolic BP †	
<130	-
130-159	-
≥160	-
NIHSS †	
0/1	-
>1	-
Relevant acute infarct on imaging	
No	-
Yes	-
Lacune on imaging	
Not visible	-
Visible	-
WMH or hypoattenuation	
Not visible	-
Visible	-
SVD score	

0	-
1	-
>1	-

† Adjustment variable

Figure 4b. Forest plot of Wei-Lachin global outcome for cilostazol versus none by subgroups. Adjusted

	Interaction p
Age †	
<60	-
60-69	-
≥70	-
Sex †	
Female	-
Male	-
Highest education †	
A-level (equivalent) or higher	-
O-level/GCSE (equivalent)	-
Primary or secondary primary school	-
Pre-morbid mRS †	
0	-
1	-
>1	-
Time stroke-baseline †	
<180 days	
180-364 days	
≥365 days	
Smoking	
Never	
Past	
Present	
Hypertension	
No	-
Yes	-
Diabetes mellitus	
No	-
Yes	-
History of stroke or TIA	
No	-
Yes	-
Systolic BP †	
<130	-
130-159	-
≥160	-
NIHSS †	
0/1	-
>1	-
Relevant acute infarct on imaging	
No	-
Yes	-
Lacune on imaging	
Not visible	-
Visible	-
WMH or hypoattenuation	
Not visible	-
Visible	-
SVD score	

0	-
1	-
>1	-

† Adjustment variable

Figure 4c. Forest plot of Wei-Lachin global outcome for combined isosorbide mononitrate and cilostazol versus neither by subgroups. Adjusted

	Interaction p
Age †	
<60	-
60-69	-
≥70	-
Sex †	
Female	-
Male	-
Highest education †	
A-level (equivalent) or higher	-
O-level/GCSE (equivalent)	-
Primary or secondary primary school	-
Pre-morbid mRS †	
0	-
1	-
>1	-
Time stroke-baseline †	
<180 days	
180-364 days	
≥365 days	
Smoking	
Never	
Past	
Present	
Hypertension	
No	-
Yes	-
Diabetes mellitus	
No	-
Yes	-
History of stroke or TIA	
No	-
Yes	-
Systolic BP †	
<130	-
130-159	-
≥160	-
NIHSS †	
0/1	-
>1	-
Relevant acute infarct on imaging	
No	-
Yes	-
Lacune on imaging	
Not visible	-
Visible	-
WMH or hypoattenuation	
Not visible	-
Visible	-
SVD score	

0	-
1	-
>1	-

† Adjustment variable

Figure 5. Forest plot of central imaging reads as per list for table 9 of absolute and change in imaging findings

- a) Isosorbide mononitrate versus none
- b) Cilostazol versus none
- c) Combined isosorbide mononitrate and cilostazol versus neither

Figure 6. Stacked distributions of 7-level ordinal cognition at 12 months

- d) Isosorbide mononitrate versus none
- e) Cilostazol versus none
- f) Combined isosorbide mononitrate and cilostazol versus neither

Figure 7. Stacked distributions of 4-level ordinal cognition at 12 months

- a) Isosorbide mononitrate versus none
- b) Cilostazol versus none
- c) Combined isosorbide mononitrate and cilostazol versus neither

Figure 8. Stacked distributions of mRS at 12 months

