Experience with cilostazol and ISMN are lacking in Europe: Despite the large amount of promising data from the Asia-Pacific region for cilostazol (Figure 1) and in European cardiology for ISMN, and both drugs being licensed in Europe for vascular indications with available generic forms, there is little experience with cilostazol for vascular disease in Europe or North America and little experience of long term administration of ISMN or related nitrate donors in any type of stroke. Therefore, information on patient tolerability (e.g. cilostazol and ISMN cause headache), safety (e.g. platelet function, postural hypotension, bleeding), markers of efficacy (reduction in stroke recurrence), or on whether both drugs can be taken together in full dose, is lacking. Information on safety is important given that a) cilostazol will need to be given in addition to guideline secondary antiplatelet stroke prevention which might increase bleeding (despite little evidence of antiplatelet effects of cilostazol combined with other antiplatelet drugs^{42,33}), and b) ISMN may reduce BP leading to postural hypotension and falls or accelerate brain white matter damage in older patients, which may concern physicians. Thus information on these points is necessary in order to justify a large Phase III trial of cilostazol and/or ISMN to prevent stroke and dementia manifestations of SVD and justify further testing of cilostazol and/or ISMN.

LACI-1 Pilot trial: The LACI-2 trial design is based on experience gained by the LACI-2 investigators with cilostazol and ISMN in patients with lacunar ischaemic stroke in a pilot trial funded by the Alzheimer's Society. LACI-1 started recruitment March 2016, is recruiting 60 patients in two UK centres (Nottingham, Edinburgh), and testing short-term dose escalation protocols for cilostazol and ISMN, individually and together, to the dose planned for LACI-2, and records tolerability, safety and early markers of efficacy.

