10.3.2 Outcome Events

The following events are **outcome events** and will be recorded as such in the eCRF. All outcome events must be assessed for seriousness and causality by the PI or a delegated trial physician. Outcome measures are not recorded as AEs or further reported to the Sponsor, unless they fulfil the criteria of seriousness as defined in section 10.1 and are deemed possibly related to the IMP. The TSC will review all outcome events six monthly blinded to treatment allocation; the DMC will review all outcomes unblinded to treatment allocation annually and on special request. These events are not of themselves reasons to automatically discontinue the trial treatment, the need for which should be assessed by the PI and attending medical staff and decisions notified to the Trials Office. The participant's wishes in the event of loss of capacity are collected on the Trial Participant Consent Form which should also be consulted.

- Bleeding
- Bruising
- Chest pain, non-specific
- Diarrhoea
- Dizziness or light headedness
- Falls
- Headache
- Heart attack
- Heartburn
- Hypotension
- Loss of mental capacity
- Nausea
- Palpitations
- Recurrent stroke or TIA

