	Moderate cognitive impairments (T-MoCA 10-14 OR TICS-m 12-16) AND Moderate dysfunction (mRS 3 or 4)	OR Any clinical diagnosis of dementia made independent of study, e.g. by memory clinic, in primary care, recording of dementia on death certification, prescription of cholinesterase inhibitor or memantine
	Severe cognitive impairments (T-MoCA <10 OR TICS-m <12) AND Severe dysfunction	

	In a care-home OR mRS 4,5	
Death	Death (mRS 6)	Death (mRS 6)

30 Harms

These are presented as serious adverse events in Tables 6a-c and 7a-c.

31 Statistical software

Statistical Analysis System (SAS) version 9.4, SAS Institute Incorporation, Cary, North Carolina.

SECTION 7. ADDITIONAL INFORMATION

Confounding covariates

The primary outcome is recruitment, and this will be tabulated; as such, there are no confounding covariates.

The possible primary outcome in any following trial will likely be a composite comprising MACE, dementia or mild cognitive impairment, non-vascular death and new MRI signs and these event rates will be assessed in the current trial. The components are likely to be correlated. Example confounding variables are given and these are categorised by whether these were 'measured', as per routine practice, or 'unmeasured'; the latter will lead to residual confounding.

Composite outcome

Measured variables: Age, highest educational attainment, main occupation, socioeconomic status, stroke severity, function at randomisation, cognitive ability at randomisation, diabetes mellitus, hypertension, smoking, carotid disease, blood pressure, prescribed medications, time from stroke to randomisation, presence of a relevant infarct and SVD lesion severity on brain imaging.

Unmeasured: Examples are social isolation, vision, hearing, cardiac function (atrial fibrillation and heart failure are documented) and post-stroke complications.

Governance

LACI-2 is funded by the British Heart Foundation (CS/15/5/31475) and approved by the East Midlands – Nottingham 2 Research Ethics Committee (Ref: 17/EM/0077). The Sponsor is the ACCORD office, University of Edinburgh and NHS Lothian. NHS Research and Development/ Innovation approval is given at each participating site. The study is adopted by the National Institute for Health Research (NIHR) Clinical Research Network in England and the Stroke Research Network in Scotland.

Minimising bias

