Respiratory	xx (xx.x)	xx (xx.x)	(xx.x, xx.x), p=0.xxx	xx (xx.x)	xx (xx.x)	(xx.x, xx.x), p=0.xxx
Gastrointestinal	xx (xx.x)	xx (xx.x)	(xx.x, xx.x), p=0.xxx	xx (xx.x)	xx (xx.x)	(xx.x, xx.x), p=0.xxx
Genitourinary	xx (xx.x)	xx (xx.x)	(xx.x, xx.x), p=0.xxx	xx (xx.x)	xx (xx.x)	(xx.x, xx.x), p=0.xxx
Secondary	xx (xx.x)	xx (xx.x)	(xx.x, xx.x), p=0.xxx	xx (xx.x)	xx (xx.x)	(xx.x, xx.x), p=0.xxx
Haematological	xx (xx.x)	xx (xx.x)	(xx.x, xx.x), p=0.xxx	xx (xx.x)	xx (xx.x)	(xx.x, xx.x), p=0.xxx
Metabolic/endocrine	xx (xx.x)	xx (xx.x)	(xx.x, xx.x), p=0.xxx	xx (xx.x)	xx (xx.x)	(xx.x, xx.x), p=0.xxx
Musculoskeletal	xx (xx.x)	xx (xx.x)	(xx.x, xx.x), p=0.xxx	xx (xx.x)	xx (xx.x)	(xx.x, xx.x), p=0.xxx
Infection/sepsis	xx (xx.x)	xx (xx.x)	(xx.x, xx.x), p=0.xxx	xx (xx.x)	xx (xx.x)	(xx.x, xx.x), p=0.xxx
Tumour/malignancy	xx (xx.x)	xx (xx.x)	(xx.x, xx.x), p=0.xxx	xx (xx.x)	xx (xx.x)	(xx.x, xx.x), p=0.xxx
Other	xx (xx.x)	xx (xx.x)	(xx.x, xx.x), p=0.xxx	xx (xx.x)	xx (xx.x)	(xx.x, xx.x), p=0.xxx
Total	xx (xx.x)	xx (xx.x)	(xx.x, xx.x), p=0.xxx	xx (xx.x)	xx (xx.x)	(xx.x, xx.x), p=0.xxx

Table 8. Targeted symptoms occurring at any time on treatment on isosorbide mononitrate (ISMN), cilostazol (cil) or both.

Data are number (%); comparison by binary logistic regression.

	ISMN	No ISMN	Difference (p)	Cil	No cil	Difference (p)	ISMN /Cil	No ISMN /Cil	Difference (p)
Headache	xx (xx.x)	xx (xx.x)	(xx.x, xx.x), p=0.xxx	xx (xx.x)	xx (xx.x)	(xx.x, xx.x), p=0.xxx	xx (xx.x)	xx (xx.x)	(xx.x, xx.x), p=0.xxx
Stopped normal activities	xx (xx.x)	xx (xx.x)	(xx.x, xx.x), p=0.xxx	xx (xx.x)	xx (xx.x)	(xx.x, xx.x), p=0.xxx	xx (xx.x)	xx (xx.x)	(xx.x, xx.x), p=0.xxx
Palpitations	xx (xx.x)	xx (xx.x)	(xx.x, xx.x), p=0.xxx	xx (xx.x)	xx (xx.x)	(xx.x, xx.x), p=0.xxx	xx (xx.x)	xx (xx.x)	(xx.x, xx.x), p=0.xxx
Stopped normal activities	xx (xx.x)	xx (xx.x)	(xx.x, xx.x), p=0.xxx	xx (xx.x)	xx (xx.x)	(xx.x, xx.x), p=0.xxx	xx (xx.x)	xx (xx.x)	(xx.x, xx.x), p=0.xxx
Dizziness	xx (xx.x)	xx (xx.x)	(xx.x, xx.x), p=0.xxx	xx (xx.x)	xx (xx.x)	(xx.x, xx.x), p=0.xxx	xx (xx.x)	xx (xx.x)	(xx.x, xx.x), p=0.xxx
Stopped normal activities	xx (xx.x)	xx (xx.x)	(xx.x, xx.x), p=0.xxx	xx (xx.x)	xx (xx.x)	(xx.x, xx.x), p=0.xxx	xx (xx.x)	xx (xx.x)	(xx.x, xx.x), p=0.xxx
Loose stools	xx (xx.x)	xx (xx.x)	(xx.x, xx.x), p=0.xxx	xx (xx.x)	xx (xx.x)	(xx.x, xx.x), p=0.xxx	xx (xx.x)	xx (xx.x)	(xx.x, xx.x), p=0.xxx

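### Hypotension is collected as an outcome event and named in the rationale as a possible ISMN harm, but no planned SAP table reports it by treatment group

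*SAP*

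**What the plan says.** **Rationale.** Protocol 1.2 includes postural hypotension in its examples of missing safety information. It gives as a specific concern that "ISMN may reduce BP leading to postural hypotension and falls or accelerate brain white matter damage in older patients", and concludes: "Thus information on these points is necessary in order to justify a large Phase III trial".

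**Recording.** Protocol 10.3.2 lists 14 outcome events for the eCRF, among them hypotension, heartburn, "Chest pain, non-specific" and "Loss of mental capacity". The rule is: "Outcome measures are not recorded as AEs or further reported to the Sponsor, unless they fulfil the criteria of seriousness". The sentence goes on to require that they also be judged possibly related to trial drug. Protocol Table 8 (safety recording requirements) agrees: an outcome event reaches an SAE form only if it is serious and potentially related. The other three combinations of seriousness and relatedness go to the eCRF only.

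**Reporting.** SAP section 30 says of harms: "These are presented as serious adverse events in Tables 6a-c and 7a-c". SAP Tables 7a-c are laid out by organ class, with separate rows only for myocardial infarction, ischaemic stroke, TIA and intracerebral haemorrhage. Non-serious symptoms are compared in SAP Table 8, "Targeted symptoms occurring at any time on treatment on isosorbide mononitrate (ISMN), cilostazol (cil) or both", for three contrasts: ISMN v no ISMN, cilostazol v no cilostazol, and both v neither.

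**The concern.** Each rule is reasonable alone. An event that is an outcome need not also be logged as an adverse event, provided that it is reported as an outcome. A harms section can be limited to serious events, provided that the common symptoms are tabulated elsewhere. Together the two rules leave a gap for any outcome event that has no row of its own. A non-serious hypotensive episode, or a serious one judged unrelated, appears in no planned table. A serious and possibly related episode is counted, but inside an organ-class row where it cannot be recognised as hypotension.

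Tolerability and safety are stated secondary objectives, and the trial is meant to inform the decision on Phase III. If the SAP is followed as written, the report will show falls and white matter change, the other two ISMN harms named in that part of the rationale, but not hypotension. Any later decision to show it would be made after the data were known.

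**Working it through.** The documents give no figure to reproduce here. The check matches the 14 events in Protocol 10.3.2 against every SAP table shell (Tables 1 to 9) and the SAP figure list.

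| Outcome event (Protocol 10.3.2) | Own row in a SAP outcome or harms table |
|---|---|
| Bleeding | Table 8 |
| Bruising | Table 8 |
| Diarrhoea | Table 8 (as loose stools) |
| Dizziness or light-headedness | Table 8 |
| Falls | Table 8 |
| Headache | Table 8 |
| Nausea | Table 8 |
| Palpitations | Table 8 |
| Heart attack | Tables 2, 3, 7 |
| Recurrent stroke or TIA | Tables 2, 3, 7 |
| Hypotension | none |
| Chest pain, non-specific | none |
| Heartburn | none |
| Loss of mental capacity | none |

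Count: 14 − 8 − 2 = 4 without a row, and 4/14 = 29%. SAP Table 8 is complete in the text, since Table 9 follows it directly, so the missing rows are not an extraction fault.

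Other routes by which hypotension might reach the report:

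1. *Adverse-event analysis.* Protocol 9.2 promises odds ratios for adverse events. By the 10.3.2 rule, these events are not adverse events unless serious and possibly related.
2. *Named comparisons.* The lists in SAP 26a and 27a do not include hypotension.
3. *Blood pressure.* SAP Table 3 compares 12-month systolic and diastolic pressure. SAP Table C schedules blood pressure at baseline and, in some centres only, at 12 months. No measurement is scheduled at weeks 1-2, weeks 3-4 or month 6, so none covers dose escalation. A group mean at one year is also not a count of events.
4. *Related rows.* Dizziness, falls and palpitations (SAP Table 8) and heart rate (SAP Table 3) bear on the question. Protocol 10.3.2 nevertheless lists dizziness, falls and palpitations as separate events from hypotension.

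None of these gives a by-arm hypotension result.

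**The case against.** The strongest reply has five parts.

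- *Indirect coverage.* Falls and dizziness, the symptoms by which hypotension would usually show itself, are compared for all three contrasts, each with a row for stopping normal activities. This stands as mitigation. A reader might infer that 12-month blood pressure is the only haemodynamic information planned; the rows above show that it is not.
- *Oversight.* A reader might infer that an excess of hypotension would go unseen. Protocol 10.3.2 has the DMC review all outcomes unblinded, annually and on request, and the TSC review them blinded every six months. The data exist and are looked at. What is missing is the planned comparison in the report.
- *Ascertainment.* The questionnaire items described in Protocol 7.1 and 7.2 do not mention hypotension. (They also omit falls and bruising, so the lists may be incomplete.) Hypotension usually needs a reading, and readings between visits would be incidental and made in an open-label trial. Detection could therefore be incomplete or differ by arm. This stands. It argues for a caveat on the row, and against attaching a power figure: the documents give no hypotension rate from which to compute one.
- *Main-paper shells.* The tables are headed as those for the main paper, and SAP section 7 foresees secondary publications. But nothing in the SAP commits any of them to these events.
- *Breadth.* Three of the four events are not in the rationale. Loss of capacity overlaps the cognition, memory-problem and dementia rows of SAP Table 3, and the more consequential cardiac outcomes are compared elsewhere. This stands: those three are for completeness.

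A reader might also infer that hypotension should be a named safety endpoint in SAP 26a. Protocol 2.2.2 does not make it one, so that would be a new choice of endpoint and not the repair of an inconsistency.

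**Conclusion.** The point holds as a reporting gap. Four of 14 collected outcome events have no row in any planned SAP table, and one of them, hypotension, is a harm on which the protocol says information is needed to justify Phase III. The conclusion rests only on matching the lists. It needs no assumption about event rates, nor does it depend on the clause in SAP 4c that gives the SAP precedence, because Protocol 9.2 does not name hypotension either.

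The size is modest. The data are in the eCRF, the oversight committees review outcome events, and indirect markers are reported. Hypotension is one of several ISMN harms named, and the others in that sentence are covered. The documents do not support saying that the information is lost or that a safety signal would be missed altogether.

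**What to change.** Add hypotension to SAP Table 8 and, for completeness, non-specific chest pain, heartburn and loss of mental capacity. A companion table of all 14 events in Protocol 10.3.2 would serve equally well. Give n (%) with 95% confidence intervals for the same three contrasts, and have SAP section 30 refer to the table so that harms are no longer defined as serious events alone.

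State under the table that the source is the outcome-event eCRF, that hypotension was not systematically measured between baseline and 12 months, and that in an open-label trial ascertainment may be incomplete or differ by arm.

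The cost is four rows, a footnote and a cross-reference, drawn from data the protocol already requires. The small downside is that the hypotension row must be read with that caveat.
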